5.6 Premature Discontinuation of the Trial

The whole trial may be discontinued prematurely in the event of any of the following:

- New information leading to unfavorable risk-benefit judgment of the IMP, e.g., due to:
 - Evidence of inefficacy of the IMP.
 - Occurrence of significant previously unknown adverse reactions or unexpectedly high intensity or incidence of known adverse reactions.
 - Other unfavorable safety findings (Note: evidence of inefficacy may arise from this trial or from other trials; unfavorable safety findings may arise from clinical or non-clinical examinations, e.g., toxicology).
- Sponsor's decision that continuation of the trial is unjustifiable for medical or ethical reasons.
- Poor enrollment of subjects making completion of the trial within an acceptable time frame unlikely.
- Discontinuation of development of the Sponsor's IMP.
- Withdrawal of IMP(s) from the market for safety reasons (applicable to trials with marketed products only).

Health authorities and independent ethics committees (IECs) / institutional review boards (IRBs) will be informed about the discontinuation of the trial in accordance with applicable regulations.

The whole trial may be terminated or suspended upon request of health authorities.

The Sponsor may terminate the study at any time once access to study treatment for subjects still benefitting is provisioned via a rollover study, expanded access, marketed product, or another mechanism of access as appropriate.

5.7 Definition of End of Trial

The end of the trial will be defined as 1 year after the last subject completes his /her end-of-treatment visit.

If the trial is not terminated for a reason given in Section 5.6, the end of the trial is defined as 1 year after the last subject has received the last dose of avelumab.

6 Investigational Medicinal Product and Other Drugs Used in the Trial

The term IMP refers to the investigational drug undergoing a clinical trial, as well as to any comparator drug or placebo (as applicable). In this trial, the IMP is avelumab and no comparator drug or placebo is involved.

6.1 Description of Investigational Medicinal Product(s)

Avelumab is a sterile, clear, and colorless solution intended for intravenous administration. It is presented at a concentration of 10 or 20 mg/mL in single-use glass vials closed with a rubber stopper and sealed with an aluminum / yellow polypropylene flip off seal.

Each single-use 10 mg/mL vial contains 80 mg of avelumab as preservative-free acetate buffered solution (pH 5.5) containing mannitol, methionine, and polysorbate 20 (Tween 20), as stabilizers.

Each single-use 20 mg/mL vial contains 200 mg of avelumab as preservative-free acetate buffered solution (pH 5.2) containing mannitol and polysorbate 20 (Tween 20), as stabilizers.

For avelumab drug product, only excipients that conform to the current European Pharmacopeia and / or the current United States Pharmacopeia are used (see the latest Investigator's Brochure for additional details).

6.2 Dosage and Administration

Subjects will receive intravenous infusion of avelumab over 1 hour (-10 minutes / +20 minutes, i.e., 50 to 80 minutes) once every 2 weeks (for subjects in the 10 mg/kg once weekly cohort, once weekly for 12 weeks, then starting with Week 13, once every 2 weeks thereafter) (refer to [Appendix I](#)). Premedication with an antihistamine and with paracetamol (acetaminophen) approximately 30 to 60 minutes prior to each dose of avelumab is mandatory (for example, 25-50 mg diphenhydramine and 500-650 mg paracetamol [acetaminophen] i.v. or oral equivalent). This regimen may be modified based on local treatment standards and guidelines, as appropriate. Modifications of the infusion rate due to infusion-related reactions are described in [Section 6.5.4](#).

The starting dose of avelumab in the dose escalation phase is 1.0 mg/kg (dose-escalation according to 3 + 3 design up to 10.0 mg/kg is intended) and the treatment cycle will be 2 weeks (14 days). The dose of avelumab in the expansion phases is 10 mg/kg.

The dose of avelumab will be calculated based on the weight of the subject determined within 72 hours prior to administration. The dose of avelumab used for the previous administration can be repeated if the change in the subject's weight is 10% or less than the weight used for the last dose calculation. Subjects will receive avelumab until confirmed progression, unacceptable toxicity, or any criterion for withdrawal from the trial or IMP occurs (see [Section 5.5](#)). Subjects who have experienced a confirmed CR should be treated for a maximum of 24 months after confirmation, at the discretion of the investigator. If the investigator believes that a subject may benefit from treatment beyond 24 months, it may be permissible after discussion with the sponsor. Subjects who experienced a CR and have already stopped treatment can resume treatment with avelumab at the same dose and schedule. Subjects re-initiating treatment should be assessed according to the Schedule of Assessments ([Appendix I](#)).

In the case of study termination (see [Section 5.6](#)), subjects continuing to benefit from study treatment may still have access to study treatment via enrollment in a rollover study if not available through some other mechanism (eg, expanded access, marketed product).

Relevant clinical laboratory results essential for patient management decisions (hematology, biochemistry, liver function tests) must be available and reviewed before administration of avelumab.

6.3 Assignment to Treatment Cohorts

The investigator or delegate will assign a unique subject identifier number to eligible subjects in chronological order at the time of informed consent signature. Subject identifiers will comprise 17 digits, the first 10 digits representing the trial number, the following 3 digits representing the site number, and the last 4 digits representing the subject number, which is allocated sequentially starting with 0001.

The Sponsor's / CRO's medical responsible must confirm enrollment and dose level after receipt of the appropriate information relating to subject entry criteria.

This trial is not randomized. Therefore, no central treatment allocation is planned.

6.4 Other Drugs to be Used in the Trial

Premedication with an antihistamine and with paracetamol (acetaminophen) approximately 30 to 60 minutes prior to each dose of avelumab is mandatory (for example, 25-50 mg diphenhydramine and 500-650 mg paracetamol [acetaminophen] i.v. or oral equivalent). This regimen may be modified based on local treatment standards and guidelines, as appropriate.

As with all monoclonal antibody therapies, there is a risk of allergic reaction including anaphylactic shock. Avelumab should be administered in a setting that allows for immediate access to an intensive care unit or equivalent environment and administration of therapy for anaphylaxis, such as the ability to implement immediate resuscitation measures. Steroids (dexamethasone 10 mg), epinephrine (1:1,000 dilution), allergy medications (i.v. antihistamines), bronchodilators, or equivalents and oxygen should be available for immediate access. Infusion of avelumab will be stopped in case of Grade ≥ 2 infusion-related, allergic, or anaphylactic reactions. Following avelumab infusions, subjects must be observed for 2 hours post infusion for potential infusion-related reactions. Please refer to the guidelines for handling of infusion-related reaction in Section 6.5.4.1.

If an allergic reaction occurs, the subject must be treated according to the best available medical practice. Guidelines for management of infusion-related reactions and severe hypersensitivity reaction according to the National Cancer Institute are found in Section 6.5.4. A complete guideline for the emergency treatment of anaphylactic reactions according to the Working Group of the Resuscitation Council (United Kingdom) and can be found at <https://www.resus.org.uk/pages/reaction.pdf>. Subjects should be instructed to report any delayed reactions to the investigator immediately.

Further precautions are provided in Section 6.5.4. For prophylaxis of flu-like symptoms, 25 mg of indomethacin or comparable non-steroidal anti-inflammatory drug (NSAID) dose (e.g., ibuprofen 600 mg, naproxen sodium 500 mg) may be administered 2 hours before and 8 hours after the start

of each dose of avelumab intravenous infusion. Alternative treatments for fever (e.g., paracetamol) may be given to subjects at the discretion of the investigator.

6.5 Concomitant Medications and Therapies

6.5.1 Permitted Medicines and Therapies

Any medications (other than those excluded by the clinical trial protocol) that are considered necessary for the subjects' welfare and will not interfere with the trial medication may be given at the investigator's discretion.

Other drugs to be used for prophylaxis, treatment of anaphylactic reactions, infusion-related reactions, severe hypersensitivity reactions / flu-like symptoms and tumor lysis syndrome are described in Sections 5.1.7.2, 6.4 and 6.5.4.

The investigator will record all concomitant medications taken by the subject during the trial, from the date of signature of informed consent, in the appropriate section of the CRF.

Any additional concomitant therapy that becomes necessary during the trial and any change to concomitant drugs must be recorded in the corresponding section of the CRF, noting the name, dose, duration and indication of each drug.

Palliative bone directed radiotherapy may be administered during the trial. The assessment of PD will be made according to RECIST 1.1 (48) and not based on the necessity for palliative bone directed radiotherapy.

6.5.2 Non-Permitted Medicines and Therapies

As stated for the exclusion criteria in Section 5.3.2, subjects must not have had chemotherapy, radiotherapy (other than palliative bone directed radiotherapy as described in Section 6.5.1), major surgery, or received another investigational agent within 28 days before the start of study treatment.

The following treatments must not be administered during the study:

- Immunotherapy, immunosuppressive drugs (i.e., chemotherapy or systemic corticosteroids except for short term treatment of allergic reactions or for the treatment of irAEs), or other experimental pharmaceutical products. Short term administration of systemic steroid (i.e., for allergic reactions or the management of irAEs) is allowed. Steroids with no or minimal systemic effect (topical, inhalation) are allowed.
- Any vaccine therapies for the prevention of infectious disease, except administration of inactivated vaccines (for example, inactivated influenza vaccine).
- Growth factors (granulocyte colony stimulating factor or granulocyte macrophage colony stimulating factor). Exception: Erythropoietin and darbepoietin alpha may be prescribed at the investigator's discretion.

Clarification of Steroid Use:

Data indicate that corticosteroids have an adverse effect on T cell function (68) and that they inhibit and damage lymphocytes (69). Furthermore, as with all immunotherapies intended to augment cell-mediated immunity, there is a risk that concomitant immunosuppressives such as steroids will counteract the intended benefit. However, studies with anti-CTLA4 compounds indicate that short term use of steroids can be employed without compromising clinical outcomes (62). Therefore, the use of steroids during this trial is restricted as follows:

- Therapeutic use: limited to the treatment of infusion-related reactions and short term treatment of ir-AEs. The course of steroid treatment should be completed as soon as clinically feasible.
- Physiologic use: replacement for adrenal insufficiency at doses equivalent to ≤ 10 mg prednisone daily are acceptable.
- Prophylactic use: prophylactic use, e.g., for the prevention of acute infusion-related reactions, constitutes concomitant use and is prohibited.

If the administration of a non-permitted concomitant drug becomes necessary during the trial, the subject will be withdrawn from trial treatment (the Sponsor may be contacted to discuss whether the trial treatment must be discontinued).

Medications others than those specifically excluded in this study (see above) may be administered for the management of symptoms associated with the administration of avelumab as required. These might include analgesics, anti-nausea medications, antihistamines, diuretics, anti-anxiety medications, and medication for pain management, including narcotic agents.

Any additional concomitant therapy that becomes necessary during the trial and any change to concomitant drugs must be recorded in the corresponding section of the CRF, noting the name, dose, duration and indication of each drug.

6.5.3 Other Trial Considerations

The following non-drug therapies must not be administered during the study (and within 28 days before the start of trial treatment):

- Major surgery (excluding prior diagnostic biopsy).
- Herbal remedies with immunostimulating properties (e.g., mistle toe extract) or known to potentially interfere with major organ function (e.g., hypericin)
- Subjects should not abuse alcohol or other drugs during the study.

6.5.4 Special Precautions

As a routine precaution, subjects enrolled in this trial must be observed for 2 hours post infusion, in an area with resuscitation equipment and emergency agents. At all times during avelumab treatment, immediate emergency treatment of an infusion-related reaction or a severe hypersensitivity reaction according to institutional standards must be assured. In order to treat possible anaphylactic reactions, for instance, dexamethasone 10 mg and epinephrine in a

1:1000 dilution or equivalents should always be available along with equipment for assisted ventilation.

Infusion of avelumab will be stopped in case of \geq Grade 2 hypersensitivity, inflammatory response, or anaphylactic reaction. The treatment recommendations for infusion-related reactions, severe hypersensitivity reactions, and tumor lysis syndrome according to the NCI are outlined in Sections 6.5.4.1, 6.5.4.2 and 6.5.4.3, respectively. All infusion-related reactions, occurring during study drug infusion or after completion of the study drug administration, should be reported as AESIs or SAEs in case any serious criterion is met (see Section 7.4.1.4).

Investigators should also monitor subjects closely for potential irAEs, which may become manifest at the earliest after weeks of treatment. Such events may consist of persistent rash, diarrhea and colitis, autoimmune hepatitis, arthritis, glomerulonephritis, cardiomyopathy, or uveitis and other inflammatory eye conditions. The spectrum of hypothetical irAEs also includes formation of auto-antibodies like ANAs or ANCAs.

6.5.4.1 Infusion-related Reactions

Premedication with an antihistamine and with paracetamol (acetaminophen) approximately 30 to 60 minutes prior to each dose of avelumab is mandatory (for example, 25-50 mg diphenhydramine and 500-650 mg paracetamol [acetaminophen] i.v. or oral equivalent). This regimen may be modified based on local treatment standards and guidelines, as appropriate. Avelumab will be administered by i.v. infusion over a 1-hour period (-10 minutes / +20 minutes, that is, 50 to 80 minutes).

A. Symptoms:

- Fever
- Chills
- Rigors
- Diaphoresis
- Headache

B. Management (see [Table 6.1](#))

Table 6.1 Treatment Modification for Symptoms of Infusion-related Reactions Caused by Avelumab

NCI-CTCAE Grade	Treatment Modification for Avelumab

Grade 1 – mild Mild transient reaction; infusion interruption not indicated; intervention not indicated.
	
Decrease the avelumab infusion rate by 50% and monitor closely for any worsening. The recommended total infusion time for avelumab should not exceed 120 minutes.

Grade 2 – moderate Therapy or infusion interruption indicated but responds promptly to symptomatic treatment (e.g., antihistamines, NSAIDs, narcotics, i.v. fluids); prophylactic medications indicated for ≤ 24 hours.
	
Stop avelumab infusion. Resume infusion at 50% of previous rate once infusion-related reaction has resolved or decreased to at least Grade 1 in severity, and monitor closely for any worsening.

Grade 3 or Grade 4 – severe or life-threatening Grade 3: Prolonged (e.g., not rapidly responsive to symptomatic medication and/or brief interruption of infusion); recurrence of symptoms following initial improvement; hospitalization indicated for clinical sequelae. Grade 4: Life-threatening consequences; urgent intervention indicated.
	
Stop the avelumab infusion immediately and disconnect infusion tubing from the subject. Subjects have to be withdrawn immediately from avelumab treatment and must not receive any further avelumab treatment.

i.v.=intravenous, NCI-CTCAE=National Cancer Institute-Common Terminology Criteria for Adverse Event, NSAIDs=nonsteroidal anti-inflammatory drugs.

Once the avelumab infusion rate has been decreased by 50% or interrupted due to an infusion related reaction, it must remain decreased for all subsequent infusions. If a subject experiences a Grade 3 or 4 infusion-related reaction at any time, the subject must discontinue avelumab. If an infusion reaction occurs, all details about drug preparation and infusion must be recorded.

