In total, 134 subjects (27.9%) treated during the dose expansion died up to the cut-off date (05 November 2014). Of these, the majority of deaths (101 deaths; 21.0%) were due to disease progression. An additional 8 deaths (1.7%) were due to TEAEs unrelated to trial treatment, 4 deaths (0.8%) were due to TEAEs related to trial treatment, and the reason for 8 deaths (1.7%) was labeled as other. The reason for 13 deaths (2.7%) was unknown at the time of the data cut-off. Of the 134 subjects who died, 53 subjects (11.0%) died within 30 days of the last administration of trial treatment. Among these deaths, 39 (8.1%) were due to disease progression, 7 (1.5%) were due to TEAEs unrelated to trial treatment, 4 (0.8%) were due to TEAEs related to trial treatment, and 3 (0.6%) were due to other reasons. No death of unknown reason was reported in the 30-day period.

Treatment-emergent AEs Leading to Permanent Discontinuation of Avelumab

A total of 80 subjects (16.7%) treated during the dose expansion withdrew permanently from trial treatment due to 1 or more TEAE. In 25 (6.6%) of these subjects, the TEAEs leading to treatment discontinuation were considered related to trial treatment by the investigator. These TEAEs were infusion-related reaction (6 withdrawals; 1.6%), GGT increased (3 withdrawals, 0.8%), dyspnea (3 withdrawals; 0.8%), and radiation pneumonitis, aspartate aminotransferase (AST) increased, hepatocellular injury, blood creatine phosphokinase increased, blood pressure increased, pneumonitis, anaphylactic reaction, food allergy, adrenal insufficiency, anemia, hypercalcemia, hyperglycemia, arthralgia, arthritis, myositis, pain, abdominal pain lower, chest discomfort, cramps and ache on back and all over body (not yet coded), encephalopathy, syncope, and flushing (1 withdrawal each; 0.3%).

Most of the events of infusion-related reaction and anaphylactic reaction that led to permanent discontinuation of trial treatment (as described above) occurred before implementation of mandatory premedication on 28 January 2014.

Immune-related Adverse Events

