5.1.4.3 Dose-Limiting Toxicity

A DLT is defined as a \geq Grade 3 adverse drug reaction (ADR) according to the NCI-CTCAE v4.0, occurring in the DLT evaluation period of the dose escalation cohorts. ADRs are defined in this trial as any AEs suspected to be related to avelumab by the investigator and / or Sponsor.

The observation period for DLTs refers to the first 3 weeks of trial drug treatment in the dose escalation part for all dose cohorts for all subjects with data used for implementing the dose-escalation algorithm for determination of the MTD. Additional subjects enrolled in the dose escalation phase will have AEs collected but will not have a specific DLT observation period. A DLT is defined as any \geq Grade 3 treatment-related toxicity confirmed by the SMC to be relevant for the study drug treatment. The SMC recognizes that in the absence of prior human experience with avelumab, a conservative approach will be adopted in ascribing the relevance of the treatment-related toxicity to drug. Treatment-related SAE will be ascribed as related to drug except where a clear relationship to the underlying disease or recognized co-morbidities is evident. For this trial, the MTD is defined as the highest dose where < 2 of 6 subjects experience a DLT.

A DLT is specifically defined as any one of the following:

Any Grade ≥ 3 toxicity that is possibly, probably, or definitely related to avelumab, occurring during the DLT evaluation period (21 days after administration of avelumab), except for any of the following:

- Grade 3 infusion-related reaction resolving within 6 hours and controlled with medical management.
- Transient (≤ 6 hours) Grade 3 flu-like symptoms or fever, which is controlled with medical management.
- Transient (≤ 24 hours) Grade 3 fatigue, local reactions, headache, nausea, emesis that resolves to \leq Grade 1.
- Grade 3 diarrhea, Grade 3 skin toxicity, or Grade 3 liver function test (ALT, AST, or GGT) increase that resolves to \leq Grade 1 in less than 7 days after medical management (e.g., immunosuppressant treatment) has been initiated.
- Single laboratory values out of normal range that are unlikely related to trial treatment according to the investigator, do not have any clinical correlate, and resolve to \leq Grade 1 within 7 days with adequate medical management.
- Tumor flare phenomenon defined as local pain, irritation, or rash localized at sites of known or suspected tumor.

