17.1 Adverse Events

The severity of AEs will be graded using the NCI-CTCAE, version 4.0 except where CTCAE grades are missing. No imputation of missing grades will be performed. AEs will be coded according to latest available version of MedDRA. AEs of special interest include IRRs and immune related adverse events (irAEs), which are detailed in Section 17.1.4 and 17.1.5, respectively.

- **Treatment Emergent Adverse Events:** TEAEs are those events with onset dates occurring during the on-treatment period for the first time, or if the worsening of an event is during the on-treatment period as defined in Section 11.
- **Related Adverse Events:** adverse events with relationship to study treatment (relationship with study treatment = related) reported by the investigator and those of unknown relationship (i.e. no answer to the question “Relationship with study treatment”).
- **Serious Adverse Events (SAE):** serious adverse events (as recorded on the AE eCRF page, serious adverse event = yes).
- **Adverse Events Leading to Treatment Discontinuation:** adverse events leading to permanent discontinuation of study treatment (as recorded on the AE eCRF page, action taken with study treatment = drug withdrawn).
- **Adverse Events Leading to Death:** adverse event leading to death (as recorded on the AE eCRF page, outcome = fatal or toxicity grade = 5).

- **Original Definition Immune Related Adverse Events (irAE):** irAEs are identified according to a pre-specified search list of MedDRA PTs, documented in a version-controlled repository maintained by the Sponsor and finalized for analysis prior to database lock. The original definition irAEs are utilized when the process for irAE medical review is either not followed or has not yet been completed for the delivery.
- **Updated Definition Immune Related Adverse Events:** irAEs according to case definition classified by medical review. Details are included in Table 15 in Appendix II.
- **Updated Definition Infusion Related Reaction:** IRRs are identified based on a list of MedDRA PTs. The detailed criteria of the timing relationship to infusion are specified in Table 16 in Appendix II.

AEs will be summarized using the MedDRA PT as event category and MedDRA primary SOC as summary category. All AE tables will be restricted to TEAEs unless otherwise specified.

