17.1.4 Infusion Related Reaction

IRRs will be summarized by the follow variables:

- Number of subjects with at least one event by the worst toxicity grade (grade 1/ grade 2/ grade 3/ grade 4/ grade 5/ missing grade)
- Number of subjects with IRR leading to permanent treatment discontinuation
- Time related to first onset (infusion 1/ infusion 2/ infusion 3/ infusion 4 or later). The events should be assigned to the actual drug infusions that the subject received, not to the planned dates. An IRR is assigned to a drug infusion if its onset is at the same date (but not before dosing) or the following day of drug infusion.
- Number of subjects with at least one event by the worst toxicity grade that occurred in the presence of premedication (grade 1/ grade 2/ grade 3/ grade 4/ grade 5/ missing grade). The denominator will be the number of subjects with at least one dose administered in the presence of pre-medication. The maximum toxicity will be derived among those IRRs that occurred in the presence of premedication.
- Number of subjects with at least one event by the worst toxicity grade that occurred in the absence of premedication (grade 1/ grade 2/ grade 3/ grade 4/ grade 5/ missing grade). The denominator will be the number of subjects with at least one dose administered in the absence of pre-medication. The maximum toxicity will be derived among those IRRs that occurred in the absence of premedication.

The listing of IRRs will be provided with the relevant information such as AE SOC/PT, start/stop date, toxicity grade, relationship to the study treatment, action taken with study treatment, outcome, premedication, and study medication batch ID etc.

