Onset	AE onset after 1st avelumab administration until up to 90 days after last dose
Duration	AE does not spontaneously resolve (i.e., without corticosteroids/ immunosuppressant treatment) within 7 days after onset
Immunosuppressive therapy	AE treated with corticosteroid or other immunosuppressant therapy. For endocrinopathies only: AE required hormone replacement* and /or (corticosteroid or other immunosuppressive therapy)

Etiology	No other clear etiology or Histopathology/biopsy consistent with immune-mediated event
All criteria listed in the left column need to be fulfilled for an event to meet the case definition of immune-mediated reaction.	
*Hormone replacement will be evaluated for specific endocrinopathy disorders only as follows: 
 • Thyroid disorders (HLT): Thyroid therapy (ATC codes (H03A, H03B)) • Diabetes mellitus (including hyperglycemia): Insulin (ATC code A10A) 	

Infusion related reactions are identified based on a list of MedDRA PTs and criteria on the timely relationship according to Table 16.

Table 16 Criteria for infusion related reactions

Infusion related reactions	
Reactions - Considered when onset is on the day of avelumab infusion (during or after the infusion) or the day after the avelumab infusion (irrespective of resolution date):
 
 • Infusion related reaction • Drug hypersensitivity • Anaphylactic reaction • Hypersensitivity • Type 1 hypersensitivity 
Signs and Symptoms - occurring on the day of avelumab infusion (during or after the infusion) and resolved with end date within 2 days after onset
 
 • Pyrexia • Chills • Flushing • Hypotension • Dyspnea • Wheezing • Back pain • Abdominal pain • Urticaria
----------------------------	---

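### The 2-day resolution limit in the expansion SAP's Table 16 keeps long, unresolved or undated symptom-coded infusion reactions out of the IRR tables; add a supplementary count for the serious ones

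*Protocol*

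**What the plan says.** Section 17.1 of the expansion SAP identifies IRRs from a list of MedDRA preferred terms and adds: "The detailed criteria of the timing relationship to infusion are specified in Table 16 in Appendix II". Table 16 has two routes.

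- **Reaction terms** (infusion related reaction, drug hypersensitivity, anaphylactic reaction, hypersensitivity, type 1 hypersensitivity). These count with onset on the infusion day "or the day after the avelumab infusion (irrespective of resolution date").
- **Signs and symptoms** (pyrexia, chills, flushing, hypotension, dyspnea, wheezing, back pain, abdominal pain, urticaria). These count only when "occurring on the day of avelumab infusion (during or after the infusion) and resolved with end date within 2 days after onset".

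Section 17.1.4 tabulates the resulting IRRs by worst grade (1 to 5, or missing), overall and split by premedication. It also tabulates "Number of subjects with IRR leading to permanent treatment discontinuation". Section 18.2 imputes incomplete AE start dates but not AE end dates.

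On the protocol side, section 6.5.4.1 lists fever, chills, rigors, diaphoresis and headache as IRR symptoms. Its Table 6.1 describes the severe category as "Grade 3: Prolonged (e.g., not rapidly responsive to symptomatic medication and/or brief interruption of infusion); recurrence of symptoms following initial improvement", and also names hospitalization. Section 6.5.4 states: "All infusion-related reactions, occurring during study drug infusion or after completion of the study drug administration, should be reported as AESIs or SAEs" when a seriousness criterion is met.

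**The concern.** On the symptom route, whether an event counts as an IRR depends on how it turned out. A chill or a drop in blood pressure that settles by the next day is an IRR. The same event, still ongoing, lasting four days or lacking an end date, is not. A fatal event is not resolved on a plain reading, so it fails as well. The condition can remove events but never add them, and it bears on the longer and unresolved ones.

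The tables built on this definition are the ones meant to show severity: worst grade up to 5 and permanent discontinuation. IRRs are an identified risk and an adverse event of special interest in this programme. The same IRR status feeds the premedication comparison in 17.1.4 and the IgE subset analysis in 16.5.1. A symptom-coded reaction missing here is missing from the summary a reader would use to judge how severe avelumab infusion reactions become.

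**Working it through.** **1. Which events fail Table 16**

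| How the event is recorded | Onset | End date | Counted as IRR? |
|---|---|---|---|
| One of five reaction terms | infusion day or next day | any or none | yes |
| One of nine symptom terms | infusion day | within 2 days of onset | yes |
| One of nine symptom terms | infusion day | later than 2 days | no |
| One of nine symptom terms | infusion day | ongoing or missing (not imputed) | no |
| One of nine symptom terms | infusion day | fatal (not resolved, on a plain reading) | no |
| Symptom term not on the list | any | any | no |

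The gap is confined to reactions recorded only as symptoms.

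**2. Does Grade 3 imply failing the 2-day limit?** No. Table 6.1 describes prolonged as a lack of rapid response to medication or interruption, and sets no number of days. The dose-limiting toxicity section (5.1.4.3) exempts a "Grade 3 infusion-related reaction resolving within 6 hours and controlled with medical management". Such an event meets the 2-day window even if it is coded as a symptom.

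**3. Symptom lists compared.** Of the five protocol symptoms, two match Table 16 (fever as pyrexia, and chills). Rigors, diaphoresis and headache are not named. If rigors are coded to chills, which the documents do not say, two are missing; otherwise three.

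**4. Are both routes in use?** Protocol section 3.4 gives related TEAEs in 480 expansion subjects:

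- infusion-related reaction: 9.8%, and 0.098 × 480 = 47 subjects
- chills: 6.9%, and 0.069 × 480 = 33 subjects
- pyrexia: 5.6%, and 0.056 × 480 = 27 subjects

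The reaction term is well used, and related symptom terms are common beside it. How many of those chills and fevers were infusion reactions is not stated.

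**5. Bound on the discontinuation count.** The inputs are the related withdrawals in protocol section 3.4 (cut-off 05 November 2014).

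- Reaction terms: 6 infusion-related reaction + 1 anaphylactic reaction = 7.
- Terms named in Table 16's symptom list: 3 dyspnea + 1 flushing = 4.
- Ceiling: 4 / (7 + 4) = 4/11 = 36%.
- Floor: 0.

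The ceiling needs all four symptom withdrawals to be separate subjects, to be infusion reactions starting on the infusion day, and to last beyond 2 days or lack a qualifying end date. The section gives no onset or end dates. It lists 6 + 3 + 3 + 22 = 34 term-level withdrawals in 25 subjects, so some subjects contribute more than one term. Only counts are used, because the percentages there do not share a denominator: 25/0.066 is about 379, whereas 80/0.167 is about 479.

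**The case against.** **Reaction terms have no duration limit, and all infusion reactions must be reported as special-interest or serious events.** This stands as a limit on scope: a reaction recorded under a diagnosis term is never lost. It does not close the gap. The protocol sentence is a reporting rule, whereas Table 16 selects on preferred term and timing. The symptom route itself presupposes that some reactions arrive as symptoms.

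**The limit has a purpose.** Among all TEAEs in section 3.4, dyspnea occurred in 11.9% of subjects, back pain in 10.8% and pyrexia in 10.4%. Dyspnea was also the most frequent TEAE of Grade 3 or higher (28 subjects). Without a limit, disease symptoms that happen to start on an infusion day would enter as IRRs. The SAP's modification history shows the IRR section was aligned to a programme-level standard, so changing it for one trial would cost comparability. Both points stand, and they argue against replacing the main definition.

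**Nothing leaves safety reporting.** A long, serious or fatal symptom still appears in the tables by term and worst grade, leading to death, leading to discontinuation, and serious (17.1.1 to 17.1.3). That is correct, but those tables do not identify it as infusion-related.

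**The protocol's symptom list is for clinical recognition and is not an analysis definition.** This is fair. Headache in particular is non-specific, which is a reason not to add it to the main definition.

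A reader might infer from Table 6.1 that prolonged reactions, and so Grade 3 reactions generally, drop out of the IRR tables. The documents do not support that: the reaction terms are exempt, and prolonged there does not mean longer than 2 days.

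**Conclusion.** The point holds for symptom-coded events only. Table 16 leaves out reactions recorded solely as listed symptoms when they outlast 2 days, are unresolved or fatal, or have no end date. For true reactions of this kind the effect on the worst-grade and discontinuation counts can only be downward.

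The size is unknown because no durations are given. The one available illustration, the related withdrawals in protocol section 3.4, gives 0 to 4 events. A reader might take 36% as an estimate of understated treatment-stopping IRRs. It is a ceiling resting on unverified assumptions about onset, duration and separate subjects. Nor do the IRR tables as a whole select for mild, short events, since the reaction-term route has no such condition. The case for acting is that the exclusion runs one way, bears on an identified risk, and can be checked with one derivation.

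**What to change.** Keep Table 16 as the main, programme-standard definition. Add to section 17.1.4 of the expansion SAP a supplementary IRR table, by worst grade and by permanent discontinuation. It would count every Table 16 IRR plus any listed symptom, regardless of end date, that meets all of these conditions:

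- onset on the infusion day, during or after the infusion;
- related to treatment, or relationship missing;
- Grade 3 or higher, serious, fatal, or leading to permanent discontinuation.

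In that table only, and under the same conditions, include the symptoms in protocol section 6.5.4.1 that Table 16 does not name: diaphoresis, headache, and rigors if these are not coded to chills.

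The cost is a paragraph of SAP text and one extra derivation. The downside is that a few related events that were not infusion reactions, such as disease dyspnea judged related, may be counted. The relatedness and severity conditions limit this, and the unchanged main table shows the difference. No clinical procedure is affected.
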